3.2 Study Outcome Measures

3.2.1 Primary

The primary endpoint will be a monthly mean pain intensity score change from baseline, representing the arithmetic mean of daily average pain intensity score values. The daily average pain intensity score will be measured on a 0-100 numeric rating scale (NRS) and reported in the Daily Symptom Diary (DSD). The monthly mean pain intensity score will be determined from baseline, for each month/cycle (4 weeks/28 days) during the 12 weeks (3 cycles) of treatment and the last month prior last visit (Follow up).

The monthly mean pain intensity score will be calculated if a participant has at least 80% compliance with the DSD.

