4 STUDY DESIGN

60 patients (30 per each arm) aged 18-65 years old of either sex, and any race or ethnicity presenting chronic painful temporomandibular disorders (TMD) will be randomly assigned in a 1:1 parallel, double-blind, phase 2 single center clinical trial, to receive either Erenumab or placebo. Participants will attend 6 clinic visits (Visit 0-Visit 5) over a period of 21 weeks. The study should be completed over a period of 3 years, with an estimated duration of recruitment of 2.5 years.

Participants will be pre-screened in person at the Brotman Facial Pain clinic, the Oral and Maxillofacial Surgery Clinic both at the University of Maryland, School of Dentistry or by telephone. Potentially eligible and interested participants will be scheduled for a Screening and Baseline Visit (Visit 0). During Visit 0, participants will provide informed consent and be evaluated for eligibility; information including demographics, medical history, concomitant medications, and therapies will be collected. In addition, participants will be assessed for pain level, pain symptoms, jaw function, health status, among other measures and a blood sample will be collected. Procedures will include clinical examinations and tests and the dispensation of various questionnaires, all of which are listed in the Schedule of Events (Appendix A).

Participants who show compliance with the Daily Symptom Diary of at least 80% and who meet the pain score (inclusion criteria) for 28 days/4 weeks (baseline period) after Visit 0, will be randomly assigned to one of two groups (Erenumab or placebo) and will be scheduled for Visit 1 within a week of randomization.

At Visit 1, randomized participants will receive the 1st cycle of management and begin a 12-week drug treatment/placebo phase that will be divided into once a month injection/cycle for a total of 3 cycles. During that period, Visits 2-4 will take place, and many of the baseline assessments will be repeated. Between visits, communication will be conducted by telephone. The final study visit, visit 5, will occur 4 weeks after the last assessment (visit 4) and 8 weeks after the last dosage of drug treatment (Visit 3).

The primary endpoint will be the change in a monthly mean pain intensity score derived from the Daily Symptom Diary. Efficacy will be evaluated as the difference between Erenumab arm and the placebo arm in the monthly pain intensity score (on a 0-100 scale) during the 12 week treatment period.

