12.2 Sample Size Considerations

The proposed sample size of 60 randomized patients split into two independent groups is based on a 30-50% reduction in TMD pain scores at follow-up, assuming a power of 90%, alpha = 0.05, assuming a 0.5 (medium) effect size. This was calculated using GPower software. This sample size is also based on the conservative assumption of a 15% patient drop out at follow up.

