12.4 Final Analysis Plan

The main goal of the statistical analyses is to estimate change in study primary and secondary endpoints to evaluate efficacy of Erenumab. Intention to treat analysis will be performed using a within-subjects student's pair t-test or repeated measures ANOVA (if more than two time points) to determine significant reduction in pain after drug intervention in each patient. Subsequently, a between-subjects unpaired t-test or two-way mixed designed ANOVA (if more than two time points) will be performed to determine difference between the placebo and erenumab groups. *Post-hoc analysis* will only be conducted following a significant ANOVA test, to protect from Type I errors. We will use a 2-way between subject's repeated measure ANOVA design to determine difference between the Erenumab group and placebo group, or a between-subjects unpaired t-test if two groups only. We will also use student's paired t-test to determine time points of significance. 50% reduction in pain days will be determined as a function of baseline pain days. Where, appropriate similar statistical procedures will be used for secondary endpoints.

Descriptive statistics for safety measures will also be calculated.

We will collect the following data for descriptive purposes and, if necessary, to use as covariates: Demographic information (age and race/ethnicity), rescue medication history, psychological factors and perceived change in overall status (PGIC).

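### Section 12.4 does not fix the time levels, outcome or tested term of the mixed ANOVA for the arm difference, and one natural reading averages untreated months into the drug effect

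*Combined protocol and SAP*

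**What the plan says.** Section 12.4 first tests for a fall in pain within each patient, by paired t-test or, with three or more time points, by repeated-measures ANOVA. For the arms it then says that an unpaired t-test or a "two-way mixed designed ANOVA (if more than two time points) will be performed to determine difference between the placebo and erenumab groups". A later sentence repeats the ANOVA but reserves the unpaired t-test for the case of only two groups, which this trial always is. The choice between the two methods therefore turns on the number of time points in one sentence and the number of groups in another.

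Section 12.4 does not list the time points, say whether the outcome is the raw monthly score or the change, or name the term to be tested. Baseline pain is not among its optional covariates. Post-hoc comparisons follow only if the ANOVA is significant.

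Other sections describe the primary comparison in different ways:
- Section 3.2.1: change from baseline in the monthly mean, determined "for each month/cycle (4 weeks/28 days) during the 12 weeks (3 cycles) of treatment and the last month prior last visit (Follow up".
- Section 4: efficacy is the arm difference "in the monthly pain intensity score (on a 0-100 scale) during the 12 week treatment period". Visit 5 falls eight weeks after the last dose.
- Section 12.1: change from Visit 1 to Visit 4.
- Section 12.3.2: change from Visit 0 to Visit 4, using the month before each visit.

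**The concern.** The within-patient test looks for a fall in pain after treatment, so it needs the pre-dose month as a time point. The between-arm sentence follows directly and uses the same condition on the number of time points. A statistician could reasonably carry the same levels across, and could add the follow-up month because section 3.2.1 scores it.

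In a two-way mixed ANOVA the group main effect is the arm difference averaged over every level of time. Randomization makes the expected difference zero in the pre-dose month. The follow-up month runs from four to eight weeks after the last injection, outside the 12-week window of section 4. Averaging either month in can pull the estimate toward zero.

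The readings differ in both estimate and power. While the text is open, the primary test could also be settled after the data are seen.

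**Working it through.** **Inputs from the plan.** 30 per arm (section 5.4.1). Section 12.2 gives "assuming a power of 90%, alpha = 0.05, assuming a 0.5 (medium) effect size" and a "conservative assumption of a 15% patient drop out at follow up".

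**Assumptions.** Two-sided test. d = 0.5 is the arm difference in each treated month, in units of the between-patient SD of one monthly mean (section 12.2 does not say what the 0.5 refers to). Equal expected arm means at baseline. Compound symmetry with correlation ρ = 0.3, 0.5 or 0.7; ρ is not in the documents.

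**The plan's own figure.** An independent two-sample comparison at d = 0.5 with 90% power needs about 86 per arm (172 in total), so the stated 60 is not reproduced. Thirty per arm gives 48% power, and 51 evaluable patients give 42%. That is a separate matter. Here it means that much of the low absolute power below comes from the sample size, so the comparison between methods is what counts.

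**Dilution.** Group main effect = mean of the monthly arm differences over the levels used. With a constant effect δ in months 1-3:

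| Levels averaged | Share of δ kept |
|---|---|
| Raw: baseline + 3 months | 3/4 = 75% |
| Raw: baseline + 3 + follow-up, no effect left | 3/5 = 60% |
| Raw: same, half the effect left | 3.5/5 = 70% |
| Raw: same, full effect left | 4/5 = 80% |
| Change scores: 3 treated months | 3/3 = 100% |
| Change scores: 3 + follow-up | 3/4 to 4/4 = 75-100% |

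These shares do not depend on ρ.

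**Power.** For the one-df tests the non-centrality is Δ/√(2V/n), with n = 30:
- Group effect, baseline + 3 months: Δ = 0.75 × 0.5 = 0.375, V = (1+3ρ)/4 = 0.475/0.625/0.775, non-centrality 2.11/1.84/1.65.
- Change in the 3-month mean: Δ = 0.5, V = (1+2ρ)/3 + 1 − 2ρ = 0.933/0.667/0.400, non-centrality 2.00/2.37/3.06.
- Same contrast with baseline as covariate: Δ = 0.5, V = (1+2ρ)/3 − ρ² = 0.443/0.417/0.310, non-centrality 2.91/3.00/3.48.
- Group-by-time, baseline + 3 months: non-central F on 3 and 174 df, λ = (n/2)·Σ(δₖ − mean δ)²/(1−ρ) = 15 × 0.1875/(1−ρ) = 4.02/5.63/9.38.

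| Test (30 per arm) | ρ = 0.3 | ρ = 0.5 | ρ = 0.7 |
|---|---|---|---|
| Group effect, baseline + 3 | 54.5% | 43.9% | 36.8% |
| Group effect, plus follow-up with no effect | 40.6% | 31.4% | 25.9% |
| Group effect, plus follow-up with full effect | 63.2% | 50.3% | 41.6% |
| Group-by-time, baseline + 3 | 35.3% | 48.0% | 72.0% |
| Group-by-time, plus follow-up with no effect | 49.1% | 65.3% | 88.4% |
| Change in 3-month mean | 50.5% | 64.5% | 85.3% |
| Baseline-adjusted 3-month mean | 81.6% | 83.9% | 92.8% |

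If change scores are averaged over the three months and a follow-up month with no effect, Δ = 0.375 and V = (1+3ρ)/4 + 1 − 2ρ. Power for that test is 43.9% at ρ = 0.5 and 64.5% at ρ = 0.7.

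With 25.5 evaluable per arm (60 × 0.85 / 2), the baseline-adjusted contrast gives 74.8/77.4/88.2% and the group effect (baseline + 3) gives 47.8/38.2/32.0%.

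**Check.** In 20,000 simulated trials (ρ = 0.7, 30 per arm), the group effect averaged 0.375 against a true 0.50, with 37% power. The change contrast averaged 0.50, with 86% power.

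**The case against.** A reader might infer that the plan does count the baseline and follow-up months, and so shrinks the drug effect by 20-40%. The documents do not say that. Sections 3.2.1 and 12.3.2 define the endpoint as a change. If change is the outcome, baseline is not a level, and the loss is 0%, or at most 25% with follow-up. The endpoints in 12.1 and 12.3.2 each compare two time points, which the first between-arm sentence of 12.4 would send to an unpaired t-test. Section 3.2.1 says only that a follow-up score is determined, and section 4 confines efficacy to 12 weeks. Group-by-time, which baseline does not dilute, could be the intended test. All of this stands.

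Nor does a power loss follow in every case. At ρ = 0.3 the group effect (baseline + 3) has slightly more power than the change score, 54.5% against 50.5%. At ρ = 0.7 with a no-effect follow-up month, group-by-time exceeds the change score, 88.4% against 85.3%.

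Two other defences help less. The post-hoc comparisons depend on a significant ANOVA, so they inherit its ambiguity, and the paired t-tests are within-arm. The protocol lists a Statistical Analysis Plan among its supplemental materials, and the model may be settled there. It is not among the documents reviewed, and section 12 itself keeps neither month out of the ANOVA.

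**Conclusion.** The concern holds as an underspecified primary test. Section 12.4 leaves open the time levels, the outcome and the tested term, and the four descriptions of the endpoint do not settle them. A loss of 20-40% is the result of one permitted reading, the group main effect on raw monthly scores with baseline as a level: 25% without follow-up, and 20-40% with it. That arithmetic assumes a constant effect over the treated months and equal expected baseline means.

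The power figures also rest on d = 0.5 per month, compound symmetry and the assumed ρ. Within those limits, the baseline-adjusted contrast over months 1-3 had the highest power at every ρ tried and estimates the 12-week effect directly. Group-by-time avoids dilution by baseline, but it is a multi-df test with no single effect estimate. The plan should be changed because a better-defined and more powerful test is available from the same data.

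**What to change.** In section 12.4, state one primary between-arm contrast of monthly mean pain over the treated month(s) that define the primary endpoint. Reconcile sections 3.2.1, 4, 12.1 and 12.3.2 so that all name the same month(s) and the same baseline.

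Adjust the contrast for baseline-month pain, either by ANCOVA or by a longitudinal model that constrains the arms to be equal at baseline. Such a model may include baseline as a response; what should be avoided is averaging baseline into the group effect. Report the Visit 4 to Visit 5 follow-up month as a separate secondary comparison.

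The cost is protocol and SAP wording, to be settled before unblinding. It needs no extra patients, visits or data.

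### Section 12.4 does not say which ANOVA effect opens post-hoc testing, so the stated Type I error protection is not assured; its paired t-tests by time point do not test erenumab against placebo

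*Combined protocol and SAP*

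**What the plan says.** Section 12.4 (Final Analysis Plan) describes two kinds of ANOVA. The first is within-subject: a paired t-test, or a "repeated measures ANOVA (if more than two time points) to determine significant reduction in pain after drug intervention in each patient". Time is its only factor. The second is between-group: an unpaired t-test, or a "two-way mixed designed ANOVA (if more than two time points) will be performed to determine difference between the placebo and erenumab groups". A mixed ANOVA yields three F tests: group, time, and group by time.

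The next sentence says that post-hoc analysis "will only be conducted following a significant ANOVA test, to protect from Type I errors". The plan then repeats the between-group purpose and adds: "We will also use student's paired t-test to determine time points of significance". No sentence names the effect that opens the gate, lists the post-hoc contrasts, or states an adjustment for them. Similar procedures are extended, where appropriate, to secondary endpoints.

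The number of time points is not settled. Section 3.2.1 defines a monthly score at baseline, in each of the three treatment months and in the follow-up month. Section 12.1 states the primary hypothesis as change from Visit 1 to Visit 4. Section 12.3.2 gives a single change from Visit 0 to Visit 4.

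**The concern.** The gate protects the comparison of erenumab with placebo only if a treatment effect has to be shown to open it. A significant time effect says only that pain changed, averaged over both arms. That can happen without any drug effect. Section 5.1 (criterion 6) and Section 7.2.1 require pain of at least 30 on the outcome scale at entry, as an average or on at least 3 days in a week, so some regression to the mean is plausible in both arms, in addition to placebo response. If the time effect counts as a significant ANOVA, month-by-month comparisons could go ahead in a null trial almost as if there were no gate.

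The paired t-tests raise a separate problem. They compare patients with their own earlier scores, so a fall shared by both arms makes them significant. Used to say at which months the drug worked, they would give the wrong answer. At stake is a null trial that reports a significant month while citing error protection.

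**Working it through.** **The plan's own figure.** The plan gives no error rate for the gated procedure, so there is none to reproduce.

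**Inputs from the documents**
- 30 per arm (Section 4). With the 15% dropout of Section 12.2, 30 × 0.85 = 25.5, so 25 per arm was also run.
- Alpha 0.05 (Section 12.2). Sidedness is not stated; two-sided was used.
- Baseline plus three treatment months, or plus the follow-up month as well (Section 3.2.1).

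**Assumptions, because the documents give no figures**
- Within-patient correlation 0.3-0.7, equal between all months (compound symmetry), and complete data.
- The same fall in both arms from the first post-baseline month, 0 to 0.8 SD. With an assumed SD of 20, a fall of 0.5 SD is 20 × 0.5 = 10 points.
- Unadjusted between-arm t-tests at each post-baseline month as the post-hoc family. The plan does not list these.

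**Rough bound.** With independent tests, the chance of at least one false result would be 1 − 0.95³ = 14.3% for three months and 1 − 0.95⁴ = 18.5% for four. Correlation between months lowers both.

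**Simulation.** 8,000 trials per scenario with no treatment effect at any time. Simulation error on a rate of 12% is 1.96 × √(0.12 × 0.88 / 8000) = 0.7 percentage points. One representative set follows: 30 per arm, baseline plus four months, correlation 0.5. Where two figures are given, the first is for tests on the monthly score and the second for tests on change from baseline.

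| Common fall (SD) | Time effect significant | False between-arm month, any effect opens gate | Group or interaction opens gate | Interaction only opens gate | Some month significant by paired test, erenumab arm |
|---|---|---|---|---|---|
| 0 | 5.4% | 6.9 / 4.8% | 6.5 / 4.2% | 2.2 / 3.8% | 7.7% |
| 0.2 | 30.2% | 9.4 / 7.9% | 6.8 / 4.5% | 2.5 / 4.0% | 42.2% |
| 0.3 | 63.5% | 12.5 / 12.2% | 6.7 / 4.5% | 2.7 / 4.0% | 66.2% |
| 0.5 | 98.6% | 14.7 / 15.5% | 6.1 / 4.3% | 2.3 / 3.7% | 95.4% |
| 0.8 | 100% | 15.7 / 14.8% | 6.6 / 4.1% | 2.1 / 3.6% | 100% |

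At 0.5 SD the ungated rates are 14.9 / 15.6%, so a gate that time can open removes almost nothing.

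**Range over the scenarios**
- Common fall of 0.5 SD or more, any effect opens the gate: the time effect is significant in 93-100% of null trials. A false between-arm month occurs in 11-14% (three treatment months) or 12-17% (with follow-up).
- Common fall of 0.2-0.3 SD: the time effect is significant in 23-87% (four time points, 30 per arm). A false month occurs in about 7-12% with three treatment months. With the follow-up month, at correlations of 0.5-0.7, the runs give 8-15%.
- Group or group-by-time gate: 4-7%. Group-by-time only: 1-4%.
- Bonferroni over the months on change scores, with a common fall of 0.5 SD or more: 4-5% even if any effect opens the gate.
- Paired tests in the erenumab arm: 84-99% at 0.5 SD, reaching 100% at larger falls.

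**Sphericity.** If the correlation instead decays as AR(1) with 0.7-0.8 (assumed), the uncorrected group-by-time F test rejects in about 6-9% of null trials rather than 5%.

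**The case against.** The strongest reply is that the gate sentence follows directly on the mixed ANOVA, whose stated purpose is the difference between placebo and erenumab, and the sentence after it repeats that purpose. A gate on group or group by time is therefore a natural reading, and it gives an error of about 1-7% under equal correlations. This stands. A reader might infer that any significant ANOVA effect opens the gate, that the time effect will nearly always do so, and that the protection therefore does not exist. The documents support none of these as stated: the text names no effect at all, and it gives no size for a common fall. Baseline is a four-week diary average, which dampens regression to the mean compared with a single-day threshold.

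Three further points stand in part. First, the plan does not list month-by-month between-arm tests, and an adjustment would bring the error back to about 5%; but neither the contrasts nor an adjustment is stated. Second, if the primary endpoint is the single change in Section 12.3.2, one unpaired t-test answers it and no gate is needed; but Section 3.2.1 defines the score month by month, and the same procedures extend to secondary endpoints. Third, a separate Statistical Analysis Plan is listed among the supplemental materials, so silence on sphericity does not show that no correction will be made.

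None of this answers the paired t-test sentence, which is stated outright and is not tied to the gate.

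**Conclusion.** The point holds as a conditional one. The protection claimed in Section 12.4 depends on which effect opens the gate, and the section does not say. On the favourable reading the error is about 1-7% under equal correlations. If time may open the gate and both arms fall by about 0.5 SD or more, the gate adds little or nothing, and unadjusted monthly between-arm tests err at about 11-14% (three treatment months) or 12-17% (with follow-up). With a smaller common fall the excess is smaller. These figures rest on assumed falls, correlations and post-hoc tests; the documents do not support an unconditional statement that protection is absent.

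The paired t-test part does not depend on how the gate is read. With a common fall of 0.5 SD or more and no drug effect, about 84-100% of trials would show a significant month in the erenumab arm, so these tests are not evidence of efficacy.

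This goes beyond missing detail: a permitted reading defeats the stated protection, and the stated rule for time points would mislead if followed. It should be corrected before unblinding. A primary analysis based on one pre-specified Visit 4 contrast would not be affected by the gate.

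**What to change.** In Section 12.4:

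1. State that month-by-month between-arm tests follow only a significant treatment contrast: either the pre-specified Visit 4 between-arm contrast or the group-by-time test. State that a significant time effect does not open the gate.
2. List the months to be compared, say whether the follow-up month is among them, and apply Holm adjustment.
3. Describe within-arm paired t-tests as descriptive only and remove them as the means of determining significant time points.
4. If the repeated-measures ANOVA is kept, apply a Greenhouse-Geisser correction.

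The cost is wording only, with no change to data collection or sample size. The downside is that fewer individual months will reach nominal significance.

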13 SOURCE DOCUMENTS AND ACCESS TO SOURCE DATA/DOCUMENTS

All information collected considered to be source of that data such as original records of clinical findings, observations, participant self-reported information, hospital and pharmacy records, medical records, laboratory and diagnostic reports, notes to file, and all other information that is necessary to reconstruct and evaluate this clinical trial, will be kept. Clinical examination, daily symptom diary, and questionnaire data will be recorded directly from the participant onto eCRFs, with the eCRFs being the source document. Study staff will have access to the records in accordance with their assigned responsibilities outlined in the Delegation of Responsibility Log.

Study staff will maintain appropriate medical and research records for this study, in compliance with ICH E6, Section 4.9 and regulatory and institutional requirements for the protection of confidentiality of subjects. Study staff will permit authorized representatives of UMB, clinical monitors, and regulatory agencies to examine (and when required by applicable law, to copy) research records for the purposes of quality assurance reviews, audits, and evaluation of the study safety progress and data validity.

